###### **4.4.2.1. Epacadostat (INCB024360)**

Site staff will dispense medication sufficient for a 3-week cycle (21 days). Subjects will be administered study drug at 300 mg oral, twice daily, continuous dosing. All twice daily doses of epacadostat will be taken orally in the morning and evening, approximately 12 hours apart without regard to food. If the morning or evening dose is missed by more than 4 hours, that dose should be skipped and the next scheduled dose should be taken at the usual scheduled time. Doses of epacadostat will be self-administered except on the day of the cycle that the patient is visiting the study clinic for infusion (Day 1 of each cycle); epacadostat will be taken prior to pembrolizumab infusion.

Epacadostat compliance will be calculated based on the drug accountability documented and monitored by the site staff (tablet counts and pill diary). The objective is 100% compliance and investigators and their staff should evaluate compliance at each visit, and take appropriate steps to optimize compliance. If the subject falls below 85% compliance, based on 2 subsequent visits,

then it will need to be addressed immediately, and could be means to remove the subject from the study.

Epacadostat will be given daily in combination with pembrolizumab every 3 weeks for up to 24 months provided subjects are receiving benefit from treatment and have not had disease progression or met any criteria for study withdrawal. Intrasubject escalation of epacadostat is not permitted. Single agent epacadostat may be continued beyond 24 months provided the patient has benefit.

Subjects will receive treatment in continuous 21 day cycles; however, treatment may include temporary interruptions to allow for resolution of certain toxicities. Interruptions from the protocol-specified treatment plan for > 12 weeks between epacadostat and pembrolizumab doses due to toxicity require consultation between Merck/Incyte and the investigator and written documentation of the collaborative decision on subject management.

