## 6. DOSE MODIFICATIONS

### 6.1. Rationale for Dose Modification(s)

Subjects may require modification of epacadostat if necessitated by drug-related AEs, including irAEs; dose reductions of pembrolizumab are prohibited.

Epacadostat Dose Level Table	
Dose Level	Dose in mg
Starting Dose (0)	300mg BID
First Dose Reduction (-1)	200mg BID
Second Dose Reduction (-2)	100mg BID

Dosing interruptions are permitted in the case of medical / surgical events or logistical reasons not related to study therapy (e.g., elective surgery, unrelated medical events, patient vacation, and/or holidays). Subjects should be placed back on study therapy within 3 weeks (~ 21 days) of the scheduled interruption, unless otherwise discussed with Merck and Incyte. The reason for interruption should be documented in the patient's study record.

In some circumstances, it may be necessary to temporarily interrupt both study treatments as a result of AEs that may have an unclear relationship to study drug(s). Treatment with both study drugs should be withheld for drug-related Grade 4 hematologic toxicities, non-hematological toxicity  $\geq$  Grade 3 (including laboratory abnormalities), and severe or life-threatening AEs.

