## 9. STUDY CALENDARS

### Schedule of Events

	Screening	Treatment Phase 				EOT	Post-Treatment	
		C1D1	C2D1	C3D1	Day 1 All Subsequent Cycles	Discontinuation Visit	Follow-Up Visits	Survival Follow-Up
Evaluation/Window	Day -28 to Day -1	Day 1	± 3 Days	± 3 Days	± 3 Days	+ 5 Days	Every 9 Weeks After Discontinuation (± 7 Days)	Every 12 Weeks (± 7 Days)
ADMINISTRATIVE PROCEDURES								
Informed consent	X							
Inclusion/exclusion criteria	X	X						
Prior medical and cancer history	X							
Concomitant medications review	X	X	X	X	X	X		
Administer Pembrolizumab 		X	X	X	X			
Administer Epcadostat 		X	X	X	X			
Survival follow-up								X
CLINICAL PROCEDURES AND ASSESSMENTS								
Comprehensive physical exam	X					X		
Targeted physical exam		X	X	X	X		X	
ECOG performance status	X	X	X	X	X	X	X	

1 Treatment cycles are every 3 weeks (~ 21 days ± 3 days).

2 Fixed dose at 200 mg per IV every 3 weeks.

3 Fixed dose at 300 mg orally twice daily every day, all 21 days of each cycle.

	Screening	Treatment Phase 				EOT	Post-Treatment	
		C1D1	C2D1	C3D1	Day 1 All Subsequent Cycles	Discontinuation Visit	Follow-Up Visits	Survival Follow-Up
Evaluation/Window	Day -28 to Day -1	Day 1	± 3 Days	± 3 Days	± 3 Days	+ 5 Days	Every 9 Weeks After Discontinuation (± 7 Days)	Every 12 Weeks (± 7 Days)
Vital signs and weight	X	X 	X	X	X	X	X	
12-lead ECG	X					X		
AE assessment		X	X	X	X	X	X	X
EFFICACY MEASUREMENTS								
Radiologic tumor assessment	X 				X 	X 	X 	
LABORATORY ASSESSMENTS								
Comprehensive serum chemistry	X	X	X	X	X	X	X	
Tumor molecular profiling 	X							

4 Height only required to be collected at Cycle 1 Day 1.

5 Initial tumor imaging will be performed within 28 days before the first dose of study treatment. A CT chest/abdomen/pelvis with IV contrast is preferred. MRI abdomen with gadolinium is acceptable for patients with contrast allergies.

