### 12.3. Secondary Analyses

Secondary efficacy analysis will be conducted for the efficacy evaluable population. Secondary endpoints and analyses are as follows:

To evaluate response rate (RR). Response will be determined by RECIST v1.1 for solid tumors. The 95% exact CI for the RR will be estimated using the Clopper-Pearson method. For objective responders, the duration of response is the time from the first objective response contributing to an objective response, to the first objective response of PD (by RECIST v1.1) occurring after the first objective response contributing to the objective response.

To evaluate overall survival (OS). Time-to-event data will be analyzed by the Kaplan-Meier method, treating subjects with no observed death or progression as censored at their last date known to be alive. For the OS analysis, the nonparametric Kaplan-Meier method will be used to estimate the survival time distribution and the median survival.

To assess the safety and tolerability of epacadostat in combination with pembrolizumab. AEs will be coded by the MedDRA, and incidences will be tabulated by preferred term and system organ class for all events, related events, and events  $\geq$  Grade 3. Severity of AEs will be based on the CTCAE v5 scale as indicated. Quantitative safety variables and their changes from baseline (laboratory, vital signs) will be summarized with descriptive statistics. Clinically significant abnormal values will be flagged and tabulated based on predefined criteria. Exposure will be analyzed by describing dose intensity, which is defined as the dose-received divided by the dose planned over a given time interval. This will be done by cycle as well as overall cycles received for epacadostat and pembrolizumab. For each cycle, incidences of dose reductions and cycle

delays will also be tabulated, by reason for the reduction or delay. The percentage of subjects with any delay and/or reduction will also be calculated.

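### Section 12.3 does not say whether held time counts in dose intensity; on the most natural reading pembrolizumab comes out at about 100% however long it was held

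*Combined protocol and SAP*

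**What the plan says.** The exposure paragraph of Section 12.3 reads: "Exposure will be analyzed by describing dose intensity, which is defined as the dose-received divided by the dose planned over a given time interval". The next sentence names the intervals: "This will be done by cycle as well as overall cycles received for epacadostat and pembrolizumab". No other interval is given. The paragraph does not say whether a missed infusion counts as a cycle with 0 mg or simply postpones the cycle.

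The same paragraph then plans per-cycle incidences of dose reductions and cycle delays ("delays will also be tabulated, by reason for the reduction or delay") and a subject-level figure: "The percentage of subjects with any delay and/or reduction will also be calculated". It plans no summary of how long delays lasted.

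The dosing rules that feed the ratio are elsewhere in the protocol:

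- **Pembrolizumab.** The Schedule of Events gives "Fixed dose at 200 mg per IV every 3 weeks", and Section 6.1 says "dose reductions of pembrolizumab are prohibited".
- **Epacadostat.** It is planned at 300 mg twice daily on all 21 days of a cycle (Schedule of Events) and may be reduced to 200 mg or 100 mg twice daily (Section 6.1).
- **Holds.** Section 4.4.2.1 says "treatment may include temporary interruptions to allow for resolution of certain toxicities". Section 4.9.2 and the imaging footnote in Section 9 expect delayed cycle starts and extended cycles.

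**The concern.** Safety and tolerability of the combination is a secondary objective (Section 1.2), and holding treatment is a main response to toxicity in Section 6. An exposure measure should therefore fall when treatment is held.

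For pembrolizumab, the ratio taken over cycles received has the same quantity above and below the line. Only an incomplete infusion can move it.

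Holds need not be short. Under Section 6.2, patients on corticosteroids for immune-related events are held until the taper ends unless otherwise approved, and the taper lasts at least 4 weeks. That is longer than one 21-day cycle. Section 4.4.2.1 requires consultation only for interruptions beyond 12 weeks.

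The question matters at this dose. Section 2.2.4 says the lower epacadostat dose went forward in melanoma because interruptions and reductions were fewer than at 300 mg twice daily.

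At stake is one descriptive summary. Two analysts could report different figures from the same data, and the more natural reading gives the less informative one.

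**Working it through.** The plan states no dose-intensity figure, so there is none to reproduce.

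**Inputs.** Pembrolizumab is planned at 200 mg every 3 weeks, with no reductions (Schedule of Events; Section 6.1). Epacadostat is planned at 600 mg per day, or 600 × 21 = 12,600 mg per cycle. Let k be the number of infusions given and H the total weeks by which cycles start late. The documents give no value for H; 3, 6 and 12 weeks are assumptions. Eight infusions correspond to the expected average participation of about 6 months (Section 4.2).

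**Pembrolizumab, three readings of the denominator**

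- Reading A, cycles received, with a hold postponing the next cycle: 200k / 200k = 100% for every H.
- Reading B, calendar time from first dose to end of last cycle: [200k / (3k + H)] / (200/3) = 3k / (3k + H).
- Reading C, a skipped infusion counted as a 0 mg cycle: 7/8 = 87.5% for one skipped of eight, and 6/8 = 75.0% for two.

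| H (weeks, assumed) | Reading A | Reading B, k = 8 | Reading B, k = 4 |
|---|---|---|---|
| 0 | 100% | 24/24 = 100% | 12/12 = 100% |
| 3 | 100% | 24/27 = 88.9% | 12/15 = 80.0% |
| 6 | 100% | 24/30 = 80.0% | 12/18 = 66.7% |
| 12 | 100% | 24/36 = 66.7% | 12/24 = 50.0% |

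A delay equal to the 4-week minimum taper, counted from the day an infusion was due, gives 24/28 = 85.7% with k = 8.

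**Which reading fits best.** Section 12.3 names only cycles as intervals and tabulates cycle delays. Sections 4.9.2 and 9 describe holds as late cycle starts or extended cycles. Nothing counts a missed infusion as a 0 mg cycle. An extended cycle lowers the ratio only if planned dose is taken as a rate over elapsed time. If it is the one infusion planned per cycle, the ratio stays at 200/200. Reading A is therefore the most natural, though not the only one available.

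**Epacadostat.** Within a cycle the ratio does respond:

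- 200 mg twice daily: 400 × 21 / 12,600 = 66.7%.
- 100 mg twice daily: 200 × 21 / 12,600 = 33.3%.
- A 7-day hold inside a cycle: 600 × 14 / 12,600 = 66.7%.

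Between-cycle time is what is lost. Take 8 cycles, the last 4 at 200 mg twice daily, with 6 weeks of hold between cycles. Dose received is 4 × 12,600 + 4 × 8,400 = 84,000 mg. Over cycles received this is 84,000 / 100,800 = 83.3%. Over 30 calendar weeks it is 84,000 / (600 × 7 × 30) = 84,000 / 126,000 = 66.7%.

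**Cohort mean, illustration only.** If 40% of patients had one such pembrolizumab hold in an 8-infusion course, the mean would be 0.6 + 0.4 × 24/(24 + H), or 95.6%, 92.0% or 86.7% for H = 3, 6 or 12, against 100% under Reading A.

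**The case against.** The strongest reply is that the plan never excludes hold time. Its definition refers to "dose intensity, which is defined as the dose-received divided by the dose planned over a given time interval", and an analyst may take that interval as calendar time, in which case the figure falls as it should. This stands: the defect is a denominator left open, not a stated exclusion. It does not remove the point, because the only intervals named are cycles.

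A reader might also infer three stronger conclusions that the documents do not support.

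- **That tolerability is overstated.** Section 12.3 also tabulates adverse events, reductions and delays by reason, and the share of subjects with any delay or reduction. A 100% intensity would appear beside the delay rate. What is missing is duration: a delay of a few days and one of 12 weeks count alike.
- **That the analysis could not show 300 mg twice daily to be undeliverable.** That is the epacadostat dose, and its reductions and within-cycle holds lower its figure on every reading. Only pembrolizumab is fixed near 100%.
- **That the 6/15 (40%) in Section 2.2.4 is a hold rate for pembrolizumab.** It counts patients who interrupted epacadostat, and Section 6.4 shows that one drug can be interrupted while the other continues. The cohort means above borrow it as an assumption.

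A last objection is that a calendar-time ratio ending with the last cycle still misses permanent discontinuation: a patient stopped for toxicity after three on-time infusions scores 100%. This is correct, and the fix allows for it.

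**Conclusion.** The point holds as an imprecise definition with a foreseeable consequence. On the most natural reading, pembrolizumab intensity carries almost no information about holds, and epacadostat intensity is too high by whatever hold time falls between cycles. For an 8-infusion course the pembrolizumab difference is 11.1, 20.0 or 33.3 percentage points for 3, 6 or 12 weeks of delay, and it is larger in shorter courses.

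These sizes rest on assumed delays, and on holds that postpone the next cycle. The documents do not allow a forecast of how many patients will be affected. Severity is minor: the summary is descriptive, no test or decision rule uses it, and the primary endpoint and sample size are untouched.

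**What to change.** In Section 12.3, define relative dose intensity for each drug as

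total dose received / (planned dose rate × time from first dose to end of last cycle),

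with all holds and delays inside that time. The planned rates are the protocol's own starting doses: 200 mg per 21 days for pembrolizumab and 600 mg per day for epacadostat. Take the end of the last cycle as its Day 1 plus 21 days, and count a skipped infusion as 0 mg received within the interval.

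Keep the per-cycle and delay tables. Add the duration of delays, and the number and percentage of patients who permanently discontinue each drug for toxicity, since the ratio does not capture them.

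The cost is a few sentences. Tabulating cycle delays already requires cycle dates; tablet counts and diaries (Sections 4.4.2, 4.4.2.1 and 4.12.2) and infused volumes (Section 4.4.2.2) are already collected. The downside is a slightly less favourable reported figure.

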#### 12.4. **Sample Size**

We will enroll 30 patients over 18 months and follow patients for at least 6 months.

#### 12.5. **Criteria for Future Studies**

If the sample size is justified by precision only, state the outcomes that constitute success. If the protocol is part of a sequence of studies, state the statistical criteria that will be applied. If this is a pilot study, state what result would convince you to begin a fully powered study.

## 14. APPENDICES

### 14.1. APPENDIX A: PARTICIPANT ELIGIBILITY CHECKLIST

Protocol Title:	Phase II Study Of Epcadostat (INCB024360) With Pembrolizumab (MK-3475) In Metastatic Or Unresectable Gastroesophageal Junction And Gastric Adenocarcinoma Requiring Paired Biopsies
Protocol Number:	IRB-40823 / GI0015
Principal Investigator:	[name]

#### I. Subject Information:

Subject Name/ID:
Gender:  Male  Female

#### II. Inclusion/Exclusion Criteria

	Yes	No	Supporting Documentation*
Inclusion Criteria			
1. Age $\geq$ 18 years of age on day of signing informed consent			
2. Be willing and able to provide written informed consent for the study			
3. Histologically or cytologically confirmed adenocarcinoma of the distal esophagus, gastroesophageal junction or stomach, including patients with HER2+ disease 
 
• Distal esophagus is defined as within 5 cm of the GEJ
 
			
4. Patients must have metastatic or unresectable disease, including those with HER2+ disease			
5. Must have progressed on at least one line of prior therapy for metastatic disease, or be intolerant to that therapy if they have not progressed; for HER2+ disease patients should have received prior trastuzumab			

6. Life expectancy of $\geq$ 12 weeks			
7. Have a performance status of 0 or 1 (ECOG)			
8. Have measurable disease per RECIST v1.1 assessed within 4 weeks prior to study entry			
9. Tumor deemed amenable to biopsy by core for metastatic site or endoscopic biopsy for primary tumor (for both before and on-treatment biopsies)			
10. Patient must be willing to undergo 2 biopsies – before and on-treatment, provided the procedure is not deemed high-risk and is clinically feasible.			

11. Demonstrate adequate organ function within 7 days before treatment initiation, as defined below:
 
 
• Absolute neutrophil count <math>\geq</math> 1500 /mcL
 
• Platelets <math>\geq</math> 100,000 /mcL
 
• Hemoglobin <math>\geq</math> 9 g/dL or <math>\geq</math> 5.6 mmol/L without transfusion or EPO dependency (within 7 days of assessment)
 
• Serum creatinine <math>\leq</math> 1.5 x ULN or measured creatinine clearance <math>\geq</math> 60 mL/min (for subjects that have creatinine levels > 1.5 x ULN)
 
• Total bilirubin <math>\leq</math> 1.5 x ULN or direct bilirubin <math>\leq</math> ULN
 
• AST and ALT <math>\leq</math> 2.5 x ULN (for subjects that have liver metastases, <math>\leq</math> 5 x ULN)
 
• Albumin <math>\geq</math> 2.5 mg/dL
 
• INR or PT <math>\leq</math> 1.5 x ULN (if subjects are on anticoagulation therapy, PT/INR must be within therapeutic range)
 
• aPTT <math>\leq</math> 1.5 x ULN (if subjects are on anticoagulation therapy, PT/INR must be within therapeutic range)
 
			
12. Female subject of childbearing potential should have a negative urine or serum pregnancy within 3 days prior to receiving the first dose of study medication. If the urine test is positive or cannot be confirmed negative, a serum pregnancy test will be required			
13. Female subjects of childbearing potential must be willing to use an adequate method of contraception			

starting with the date of consent through 120 days after the last dose of study medication			
14. Male subjects of childbearing potential must agree to use an adequate method of contraception starting with the date of consent through 120 days after the last dose of study medication			
15. Must be able to swallow pills			
Exclusion Criteria			
1. Is currently participating and receiving study therapy or has participated in a study of an investigational agent and received study therapy or used an investigational device within 4 weeks of the first planned dose of treatment			
2. Has known hypersensitivity to pembrolizumab and/or epacadostat or any of their excipients			
3. Has had a prior anti-cancer monoclonal antibody within 4 weeks prior to day 1 or who has not recovered (i.e., $\leq$ grade 1 or to baseline) from AEs due to agents administered more than 4 weeks earlier. 
 
• Denosumab for treatment for bone metastases is allowed
 
			
4. Has had prior chemotherapy, targeted small molecule therapy, or radiation therapy within 2 weeks prior to study day 1 or who has not recovered (i.e., $\leq$ grade 1 or to baseline) from AEs due to previously administered agents 
 
• Subjects with <math>\leq</math> grade 2 neuropathy are an exception to this criterion and may qualify for the study
 
• If subjects have received major surgery, they must have recovered adequately from surgery prior to starting therapy
 
			
5. Patients who have been treated on any Merck-sponsored pembrolizumab containing gastric cancer pivotal trial will require prior authorization by Merck in order to enroll in this study			
6. Prior therapy with IDO-inhibitors			
7. Has active autoimmune disease that has required			

systemic treatment in the past 2 years (i.e., with use of disease modifying agents, corticosteroids, or immunosuppressive drugs).
 
 
• Replacement therapy (e.g., thyroxine, insulin, or physiologic corticosteroid replacement therapy for adrenal or pituitary insufficiency etc.) is not considered a form of systemic treatment
 
			

8. Has known history of, or any evidence of active, non-infectious pneumonitis
			

9. Has received a live vaccine within 30 days of planned start of therapy
 
 
• Seasonal influenza vaccines for injection are generally inactivated flu vaccines and are allowed; however intranasal influenza vaccines (e.g., FluMist®) are live attenuated vaccines and are NOT allowed
 
			

10. Has known active central nervous system (CNS) metastases and/or carcinomatous meningitis
 
 
• Subjects with previously treated brain metastases may participate provided they are stable (without evidence of progression by imaging for at least 4 weeks prior to the first dose of study treatment and any neurologic symptoms have returned to baseline), have no evidence of new or enlarging brain metastases, and are not using steroids for at least 7 days prior to study treatment
 
• Carcinomatous meningitis is excluded regardless of clinical stability
 
• Patient with prior CNS metastases treated w/ prior RT will also need: A. 2 months off RT before starting study or 4 weeks following XRT if MRI is stable and the patient is off steroids, B. Baseline MFI with no edema., and C. stable for at least 8 weeks.
 
			

11. Has known additional malignancy that is progressing or requires active treatment
 
 
• Exceptions include: basal cell carcinoma of the skin, squamous cell carcinoma of the skin, or in situ cervical cancer that has undergone potentially curative therapy
 
			

12. Has active infection requiring systemic therapy			
13. Has a known history of active TB (bacillus tuberculosis)			
14. Has known active Hepatitis B (e.g., HBsAg reactive) or Hepatitis C (e.g., HCV RNA [qualitative] detected)			
15. Has a diagnosis of immunodeficiency or is receiving systemic steroid therapy or any other form of immunosuppressive therapy within 7 days prior to the first dose of study treatment			
16. Has a known history of Human Immunodeficiency Virus (HIV) (HIV 1/2 antibodies)			
17. Is pregnant or breastfeeding, or expecting to conceive or father children within projected duration of the study, starting with pre-screening or screening visit through 120 days after the last dose of study treatment			
18. Has had Monoamine oxidase inhibitors within 21 days before screening			
19. Has any history of serotonin syndrome after receiving 1 or more serotonergic drugs			
20. Has presence of a gastrointestinal condition that may affect drug absorption			
21. Use of systemic corticosteroids			
22. Has history or presence of an abnormal ECG which, in the investigator's opinion, is clinically significant. QTcF > 480 ms or presence of a Left Bundle Branch Block (LBBB). If the QRS duration > 120ms, the JTc can be used in place of the QTcF, The JTc must be < 340 ms.			
23. Has history or current evidence of any condition, therapy, or laboratory abnormality that might confound the results of the study, interfere with the subjects participation for the full duration of the study, or is not in the best interest of the subject to participate, in the opinion of the investigator			
24. Has known psychiatric or substance abuse disorders that would interfere with cooperation with the requirements of the study			
25. Has known allergy or reaction to any component of either study drug or formulation components			

\*All subject files must include supporting documentation to confirm subject eligibility. The method of confirmation can include, but is not limited to, laboratory test results, radiology test results, subject self-report, and medical record review.

